### 1. Issue:

*Chlamydia trachomatis* (CT), *Neisseria gonorrhoeae* (NG), and syphilis (caused by *Treponema pallidum*) are bacterial sexually transmitted infections (STIs) and are neglected causes of adverse neonatal outcomes. According to WHO modelling estimates, CT, NG, and syphilis are among the most common STIs globally. These infections are even more common among people living with HIV. The risk of vertical transmission during delivery is about 50%. HIV-infected pregnant women with CT, NG, and/or syphilis infections are at increased risk of MTCT of HIV. Other studies on CT and NG infections in neonates are over 20 years old and those infections are not systematically measured in sub-Saharan Africa and are largely unknown.

Few countries provide routine antenatal testing for CT and NG. In most countries, including Botswana, the syndromic approach is used, which utilizes an algorithm to classify symptoms into STI syndromes and provide standardized treatment. Syndromic management lacks specificity and causes pregnant women to be unnecessarily exposed to antibiotics, and has low sensitivity, missing asymptomatic infections, putting neonates at risk. A study in Botswana found that among women with confirmed CT, NG, *Trichomonas vaginalis* (TV), only 10% reported vaginal discharge and 8% reported lower abdominal pain. In our pilot study, we found that less than 40% of women with etiologically diagnosed CT, NG, and TV infections reported having vaginal discharge, lower abdominal pain, and/or

painful urination. Thus, it's possible that many infections are being missed among pregnant women in Botswana. While testing for syphilis is a routine part of antenatal care in Botswana, previous studies have shown that testing coverage and receipt of treatment are suboptimal.

Our proposal has four specific aims. **Aim 1:** We will determine the burden of CT and NG infections and correlates of infection among asymptomatic pregnant women in Gaborone, Botswana by a) using diagnostic testing to estimate the prevalence of CT and NG infections at three time points: 1) first antenatal care visit, 2) third trimester antenatal visit, and 3) postnatal visit. We will also estimate the incidence of CT/NG infections between those visits and b) assess the correlates of infection. **Aim 2:** Will compare longitudinal neonatal outcomes for pregnant women tested for CT and NG infections during antenatal care with women who received standard antenatal care by a) estimating the frequency of vertical transmission of CT and NG infections and neonatal outcomes and the association with testing and treatment; and b) assessing independent factors that may be predictive of adverse neonatal outcomes. **Aim 3:** We will assess the burden of infection and markers of inflammatory response to CT and NG infection during pregnancy and associations with vertical transmission of CT and NG by a) testing immunologic factors associated with vertical transmission of CT and NG; b) determining the association between the Xpert® CT/NG assay's pathogen-specific cycle threshold value (Ct) and transmission; and c) evaluating the frequency and distribution of Sample Adequacy Control (SAC) cycle threshold values (Ct) from the Xpert® CT/NG assay, and evaluate any correlations with the transmission of CT/NG to neonates. **Aim 4:** We will determine the acceptability, feasibility, and costs of implementing point-of-care (PoC) syphilis testing and treatment among pregnant women in Gaborone, Botswana by offering: 1) dual HIV and syphilis PoC testing for pregnant women who are HIV uninfected/undiagnosed and 2) PoC syphilis testing for pregnant women with a known HIV infection with same-day treatment.

[figure not shown]
We will provide evidence to help evaluate the effects of testing on vertical CT/NG transmission and clinically important neonatal health outcomes, and to evaluate and understand biological correlates of CT/NG transmission.

## 2. Specific Aims:

- a. **Specific Aim 1:** To determine the burden of CT, NG infections and correlates of infection among *asymptomatic* pregnant women in Gaborone, Botswana.
  - i. 1(a): Use diagnostic testing to estimate the prevalence of CT/NG infections at the 1st antenatal care visit, a 3rd trimester visit, and the 1st postnatal care visit; and estimate the incidence of infections between those visits.
  - ii. 1(b): To assess the correlates of infection, including sociodemographic and behavioral factors (e.g. alcohol use), obstetric and medical information (e.g. HIV status), and sex partner characteristics.
- b. **Specific Aim 2:** To compare longitudinal neonatal outcomes for pregnant women tested & treated for CT/NG infections during antenatal care with women who received standard antenatal care.
  - i. 2(a): To estimate the frequency of vertical transmission of CT/NG infections and subsequent neonatal outcomes (e.g. ophthalmia neonatorum) and the association with maternal testing and treatment during antenatal care.
  - ii. 2(b): To assess independent factors that may be predictive of adverse neonatal outcomes and control for these factors in the analysis. Exposure measures will include maternal sociodemographic and behavioral factors (e.g. alcohol use), obstetric and medical information (e.g. HIV status), partner characteristics, and adverse perinatal outcomes (e.g. low birth weight).

- c. **Specific Aim 3:** To assess the burden of infection and markers of inflammatory response to CT/NG infection during pregnancy and associations with vertical transmission of CT/NG.
  - i. 3(a): To test immunologic factors associated with vertical transmission of CT/NG by describing concentrations of genital inflammatory cytokines in participants who test positive for CT/NG.
  - ii. 3(b): To determine the association between the Xpert® CT/NG assay's pathogen-specific cycle threshold value (Ct), a possible marker for burden of infection, and vertical transmission of CT/NG to neonates.
  - iii. 3(c): To evaluate the frequency and distribution of Sample Adequacy Control (SAC) cycle threshold values (Ct) from the Xpert® CT/NG assay, which are a measure of tissue inflammation, and evaluate any correlations with the transmission of CT/NG to neonates.
- d. **Specific Aim 4:** To determine the acceptability, feasibility, and costs of implementing point-of-care (PoC) syphilis testing and treatment among pregnant women in Gaborone, Botswana.
  - i. 4(a) To assess the acceptability and feasibility of PoC syphilis testing and treatment. (Dual HIV and syphilis PoC testing will be offered to pregnant women who are HIV uninfected/undiagnosed and rapid syphilis testing for pregnant women with a known HIV infection). Our primary outcome will be defined as acceptability of testing, which is the proportion of women tested out of all those eligible and seeking care in the study clinics. Secondarily, we will assess the proportion of women who received treatment among those with a reactive syphilis test result. We will assess any treatment, treatment completion, and time to treatment.
  - ii. To evaluate the unit costs and patient costs associated with antenatal PoC syphilis testing and treatment compared to the standard of care the standard of care.

Flow diagram

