**Laboratory Testing :** Once the specimen is collected, study staff will follow instructions for sample preparation and testing. Luminex assays enable fast and accurate cytokine measurements by utilizing specially prepared microspheres, internally dyed with a graded mixture of red or infrared fluorescent dyes. Varying the degree to which the beads are internally dyed creates hundreds of different fluorescent profiles that can be individually interrogated and classified in a single sample. The BHP lab in Gaborone can conduct cytokine analysis using an ELISA quantitative; however, this assay is currently limited to only IL-6, ICAM1, and VCAM. Further, the ELISA is a single assay and sample processing would be costly and time-consuming compared to the Luminex multiplex assay.

**Specific Aim 4:** To determine the acceptability, feasibility, and costs of implementing point-of-care (PoC) syphilis testing and treatment among pregnant women in Botswana by offering: 1) dual HIV and syphilis PoC testing for pregnant women who are HIV uninfected/undiagnosed and 2) PoC syphilis testing for pregnant women with a known HIV infection with same-day treatment to women in the designated PoC clinic. PoC testing will be offered in addition to routine syphilis and HIV testing.

**Methods and Procedures:** An additional 200 antenatal patients at the designated PoC clinic and 200 at the ‘standard of care’ clinic will be enrolled (400 total). In the PoC clinics, participants who are HIV uninfected/ undiagnosed will be offered PoC dual HIV/syphilis testing and women living with HIV will be offered a PoC syphilis test. PoC participants will receive same-day results and treatment. Participants in the standard of care clinic will continue to receive the usual care.

Additionally, analysis will incorporate the data from 200 participants previously enrolled in the CT/NG parent study. These data will be used as a “pre-test” and will include all 100 women enrolled in the standard of care clinic and all 100 women enrolled in the PoC testing clinic.

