**Reporting and Treatment:** PoC Results: All participants will receive results in person, on the same day as testing. Treatment: Appropriate clinical staff will provide treatment per the Botswana MoH STI treatment protocols (see Treatment section below). Test results will be recorded in the participant obstetric record, clinic records, as well as into the study data form. Partner Services will be offered in the same manner as Aim 1; however, expedited partner treatment will not be an option for syphilis treatment. Standard of Care: Participants will continue to receive syphilis testing per Botswana national guidelines, which includes a VDRL/RPR test at the first ANC visit with delayed results and treatment. Typically, blood specimens are sent to a central lab for processing and results are provided to clinic staff after at least three days. Women are called to return to the clinic for receipt of results. Test results and treatment are recorded in the patient-held and clinic records.

**Data collection:** For participants in the PoC clinic, acceptability of PoC syphilis testing and receipt of treatment (with dates) will be recorded by study staff in study documents, and the patient-held and clinic records. Participants who decline and reasons for decline will be recorded in study records. For participants in the standard of care clinic, the patient-held and clinic obstetric records will be reviewed to identify receipt and dates of syphilis testing and treatment. We will also abstract obstetric and health information (para, gravida, gestational age, HIV status, antiretroviral treatment) from the records of all participants. At the time of enrollment, participants will be asked to respond to a short interviewer-administered questionnaire to collect basic sociodemographic information and costs incurred related to syphilis testing. Participants will also respond to another short survey on costs during their third trimester, which will be conducted over the phone. Cost-related questions will inquire about travel, overnight lodging, out-of-pocket care costs; and the opportunity costs associated with travel, wait, and appointment times. Participants testing positive will be eligible to participate in a brief semi-structured interview on partner notification and treatment.

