To assess differences in receipt of syphilis testing, we will use a difference-in-difference (DiD) strategy, which takes the difference between two before and after differences (pre-post-test with comparison).[25] DiD will be performed using a logistic regression model with a variable for whether the individual was in the PoC clinic (PoC), whether or not it is the post period (Post), an interaction variable for the product of those two variables, and covariates. The primary outcome (Y) is the proportion of eligible women who are tested for syphilis at their first ANC visit:

$Y=a+bPoCPoC+bPostPost+bint(Post*PoC)+bcovariates$  Models will also be stratified by HIV status to see if PoC had a differential impact among WLH. Variables for which there were significant differences between the intervention and comparison group will be included in multivariable model.

Secondarily, will also assess receipt of treatment using DiD analysis by comparing the pre-test and post-test differences in terms of the proportions of participants who had a reactive test who: 1) received the first dose of treatment, and 2) completed treatment. Prevalence of syphilis will also be reported according to treatment group and HIV status as the proportion of individuals testing positive divided by the number of individuals tested. Exact binomial 95% confidence intervals for prevalence will be estimated. All analyses will be conducted with Stata 17.0 (Stata Corporation, College Station, TX).

To compare differences in costs, recurrent costs will be calculated per test, and capital and training costs will be summed and divided by the number of women tested. Those costs will be added to get an average unit cost for each strategy. For the intervention strategy, we will also calculate the average cost by HIV status at first ANC (i.e. the cost of delivering the dual HIV/syphilis test and the rapid syphilis). We will compare the mean costs using the non-parametric Mann-Whitney U test. For hypothesis 4, patient costs will be summed and an average patient cost will be calculated for each strategy, which will be compared using either the Mann-Whitney U test or Student's t-test. Cost components will be examined to determine key cost drivers and to identify potential efficiencies that could be achieved in future scale-up.

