**Specific Aim 3** At the baseline, third trimester and postnatal care study visit, self- collected swabs  and plasma samples (2-4mL) will be collected from participants in the STI testing group, and used to measure cytokine concentrations. Cytokines will be identified using the Luminex xMAP® 48-plex assay method located at Stanford University in order to test immunologic factors associated with vertical CT/NG transmission by describing concentrations of inflammatory cytokines in participants who tested positive for CT/NG. We will also conduct a secondary analysis of data collected during maternal CT/NG testing at the first postnatal visit (Aim 2) will be performed to determine the association between the Xpert® CT/NG assay’s pathogen-specific cycle threshold value ( $C_t$ ), which is a marker for the burden of infection, and vertical transmission of CT/NG to neonates; and assess the frequency and distribution of Sample Adequacy Control (SAC) cycle threshold ( $C_t$ ) values from the Xpert® CT/NG assay, which may be a marker of inflammation, and evaluate correlations with the transmission of CT/NG to neonates.

**Specific Aim 4:** Women in the syphilis sub-study will be similarly recruited and enrolled as in Aim 1 and 2. All participants will receive the standard of care in Botswana for syphilis testing with additional IPV screening and partner services offered to those in Aims 1 and 2. A simplified data collection instrument will be used to collect sociodemographic and behavioral factors, and obstetric/medical information with additional questions related to patient costs incurred due to syphilis care. Participants recruited into the PoC syphilis testing clinic will provide a blood sample for PoC syphilis testing and treatment.

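### Aim 4 patient costs are compared between the PoC and standard-of-care clinics without adjustment or a baseline, so a catchment difference in travel or time cost cannot be separated from a PoC effect

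*Protocol*

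**What the plan says.** The objective is in Protocol section 2, Aim 4: "To evaluate the unit costs and patient costs associated with antenatal PoC syphilis testing and treatment compared to the standard of care". The method is in section 3, Aim 4.

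- **Allocation.** Under Methods and Procedures, enrolment is by clinic: "An additional 200 antenatal patients at the designated PoC clinic", and 200 at the standard-of-care clinic. Nothing is randomised.
- **What is costed.** Under Data collection: "Cost-related questions will inquire about travel, overnight lodging, out-of-pocket care costs; and the opportunity costs associated with travel, wait, and appointment times".
- **When.** "At the time of enrollment, participants will be asked to respond to a short interviewer-administered questionnaire to collect basic sociodemographic information and costs incurred", and later "Participants will also respond to another short survey on costs during their third trimester, which will be conducted over the phone". Section 6 describes the Aim 4 instrument as a simplified one "with additional questions related to patient costs incurred due to syphilis care".
- **How it is analysed.** In the last paragraph under Analysis, "patient costs will be summed and an average patient cost will be calculated for each strategy". The two strategies are then tested against each other with a Mann-Whitney or a t-test. No covariate, baseline term or sensitivity analysis is given for costs.
- **Where else it enters.** Under Outcomes, the primary cost outcome is the average unit cost per woman tested, with patient and health-system costs combined.

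For receipt of testing, the same Analysis section uses difference-in-differences with covariates over four groups (100 pre-test and 200 post-test women per clinic). It uses difference-in-differences for treatment too. The SAP's economic plan covers the CT/NG intervention only.

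**The concern.** Clinic and strategy coincide, so any fixed difference between the two clinics' populations or locations is also a difference between strategies. The protocol takes account of this for testing and treatment, where the pre-test groups remove a constant clinic difference. Patient cost is at least as open to it, because fares, journey time and the value of a woman's time can differ by catchment whatever test is used.

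A pre-period contrast for costs appears to be unavailable. The pre-test women come from the CT/NG parent study. The survey topics listed for that study (section 3, Aim 1, Data collection) include no costs, and the cost questions are presented as additions for Aim 4.

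At stake are the stand-alone patient-cost comparison and the patient share of the primary cost outcome. Either could show a difference in either direction that owes nothing to PoC testing.

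**Working it through.** The documents give no standard deviation, expected difference or power for the cost comparison, so there is no planned figure to reproduce. The following shows how sensitive the stated test is.

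**Input from the protocol:** 200 women per clinic.

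**Assumptions:** two-sided 5% test; no PoC effect; lognormal cost with coefficient of variation (CV) 1.0 among women who incur any cost; the same share *p* of women with a cost in both clinics; mean cost among them differing between catchments by a fraction *r*. Neither *p* nor *r* can be taken from the documents.

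**Approximation.** Let *m* be the mean cost among women with a cost.

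- With CV 1.0, the mean square among them is 2*m*².
- Over all women the mean is *pm* and the variance is (2*p* − *p*²)*m*².
- The standardised shift is d = *rp* / √(2*p* − *p*²).
- The chance of a significant result in the expected direction is about Φ(d√(200/2) − 1.96) = Φ(10d − 1.96).

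At *r* = 10%:

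- *p* = 1: d = 0.10/1 = 0.10, giving Φ(−0.96) ≈ 17%.
- *p* = 0.5: d = 0.05/0.866 = 0.058, giving Φ(−1.38) ≈ 8%.
- *p* = 0.05: d = 0.005/0.312 = 0.016, giving Φ(−1.80) ≈ 4%, or about 5% with the opposite tail.

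**Simulation** (4,000 runs per setting), rejection rates at *r* = 10% / 20% / 30%:

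| Share with any cost | Mann-Whitney | t-test |
|---|---|---|
| All | about 20 / 57 / 86% | about 16 / 46 / 76% |
| Half | about 6 / 8 / 13% | about 9 / 17 / 32% |
| 5% | about 5% throughout | about 5% throughout |

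Spread matters too. With every woman incurring a cost, a 10% difference and a log-scale SD of 0.7 to 1.0, Mann-Whitney rejects in 16–26% of runs.

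**Could difference-in-differences be used instead?** With 100 pre-test women per clinic its standard error would be SD × √(2/200 + 2/100) = 0.173 SD, against SD × √(2/200) = 0.100 SD for the post-only contrast. The difference detectable with 80% power would rise from 0.28 SD to 0.49 SD. The data for it do not appear to exist.

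**The case against.** The strongest reply is that the protocol does not ask for raw visit costs. The enrolment questions concern costs related to syphilis testing, and section 6 ties them to syphilis care. On that reading many women may report nothing, and the table shows the false-positive risk falling towards nominal. This stands as a limit on the size. It does not settle the matter: the test is done at the first antenatal visit, so travel and waiting are shared with routine care, and no rule says how much to attribute to syphilis.

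Two features help in part. All women must live in Gaborone through delivery and the first postnatal visit, which may narrow any travel difference. The Analysis section also plans to examine cost components, which could reveal a travel-driven gap. Neither removes it from the comparison. Waiting and appointment time are also places where on-site testing could have a real effect, so not every clinic difference in time is bias.

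A reader might go further and reason that, with prevalence below 5%, PoC can save at most about 0.05 visit per woman, so that a modest catchment difference would swamp it. The documents do not support this. The account of standard care under Reporting and Treatment says women are called back for results and does not restrict this to reactive women. PoC participants also have the routine laboratory test, so the true saving is unknown.

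**Conclusion.** The concern holds as a matter of identification. The stated analysis cannot distinguish a catchment difference in travel or time cost from an effect of PoC testing, and nothing elsewhere in the protocol or SAP repairs this. Its size is unknown. Under the assumptions above, the Mann-Whitney false-positive rate runs from nominal to about 86%, driven by the share of women with any cost and by a catchment gap the documents do not quantify.

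Two stronger readings should be avoided. One is that a catchment difference will be mistaken for a PoC effect: no such difference is documented, and its direction is unknown. The other is that the pre-test groups certainly have no cost data. That is inferred from the topic list and the description of the Aim 4 instrument; the questionnaire is an attachment not available here.

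Aim 4's primary outcome is acceptability of testing, and costs are additional outcomes. The analysis should be changed, but the aim's main result is unaffected.

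**What to change.** Revise the cost paragraph of Protocol section 3, Aim 4, Analysis:

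1. For each woman, count syphilis-attributable visits, time and out-of-pocket items under a written attribution rule.
2. Value them with one set of unit costs pooled over both clinics.
3. Compare mean cost with a bootstrap confidence interval, adjusted for sociodemographic variables already collected at enrolment. Use the same valuation for the patient part of the primary cost outcome.
4. Report each clinic's own raw costs by component, descriptively.
5. Describe the result as a comparison between clinics. Common prices do not remove differences in minutes waited, and clinic and strategy remain aliased.

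Adjusting total cost for the woman's own travel cost should not be the fallback, because travel cost is part of the same outcome.

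The change needs analysis wording and a little recoding of survey items. The drawback is that the headline figure no longer reflects each clinic's local travel prices; the descriptive table keeps that information.
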